5.1 Study Design

Aim 1

The study design is a retrospective case control study of electronic health record data from the VINCI-CDW. The study will obtain data on all patients at VA who were tested for COVID-19 since February 2020 (from the VA COVID-19 Shared Data Resource in CDW). We will derive appropriate controls for our different analyses using data for all VA enrollees who were enrolled in VA care since February 2020 from CDW. There is no direct contact with patients.

Aim 2

We will measure clinical outcomes and sources of their variation using existing secondary data from Aim 1, and through a prospective structured survey (Aim 2). For Aim 1 and 2, we will initially conduct descriptive analyses of outcomes within Veterans with COVID-19, then subsequently define causal effects and causal moderation for subsets of pre-specified outcomes.

We have used this approach—use the VA secondary data to identify precisely eligible patients (so no screening questionnaires are asked of patients who are ultimately ineligible), followed by mail and telephone information and

[figure not shown]
recruitment after hospital discharge—successfully in VA Ann Arbor studies including ResCU 1, ResCU 2 (IIR's 13-079 and 17-045, approved Protocols 1597244 and 1597246).

A driving finding in VA research for the last decade has been that there is unequal and incomplete access to the benefits of VA care. EHR data by definition are only available for Veterans who have accessed care in the VA, including VA community-based care and contracted care. Other Administrative data (e.g., claims data for Medicare, Medicaid) are not available in real-time, given our dependency on other entities (i.e., CMS and VIReC) for production and linkage. Further, many important measures are not systematically ascertained or entered into the EHR in a uniform fashion for all patients. Therefore, prospective primary data collection from Veterans is necessary to define measures that are poorly captured in the VA EHR including care received at non-VA sites, caregiving receipt, disability, and employment/role function and financial toxicity, and unmet care needs in order to ensure the relevance of the work being done here. In general, we will seek to survey Veterans at 12, 18, 24, 30, and 36 months after their initial SARS-CoV-2 infection, enrolling new patients as the epidemic continues, and following patients longitudinally. The key variables of interest from new survey data for the LTO are shown in Table 2 below.

Concept	Instrument	# of items (Approx)			
Activity + Quality of Life	Activities of Daily Living (ADL) and Instrumental Activities of Daily Living (IADL); EQ-5D-5L	18			
Participation	Life Space Mobility	9+			
Employment	Health and Retirement Study's Job Status Form	1			
Financial Toxicity	NHLBI COVID-19 Financial Toxicity scale	10			
Mental Health	PHQ-9 Depression Symptoms scale	9			
Unmet Need	PROMISE instrumental support	4			
Non-VA Healthcare	VIREC Utilization Measures	2			
Fatigue + Symptoms	PROMIS Fatigue Short Form 7a; open-ended questions	9			

Aim 2 Study Population: The population of Veterans eligible for random sampling into the survey will be the same as those eligible for inclusion in Aim 1. Therefore, all data from Aim 1 will be linkable to survey responses via a cross walk.

Cases: Our primary case definition are Veterans infected with SARS-CoV-2, as defined by the standard locally available test at the time of their infection, and identified within the COVID-NST. We will restrict to Veterans seeking primary care in VA. Viral infection index date will be defined as the date of sample collection for each

patient's first positive test. We will conduct stratified random sampling with differential survey weights so that cases are equally divided based on maximal severity of their acute COVID course in VA to include members of the following mutually exclusive groups based on patterns of health care utilization within the first 30 days after initial infection with SARS-CoV-2: not hospitalized in VA; hospitalized in VA but not mechanically ventilated; mechanically ventilated. Stratified random sampling with variable sampling weights offers two advantages: (1) sampling weights assure that the aggregated population results are still representative of the study population as a whole; while (2) ensuring adequate representation to support comparisons across these subgroups of interest. Stratum- and wave-specific sampling fractions will be chosen based on data on survival to the relevant time-point in.

In general, we will organize the sampling of cases (and later of comparators) around the waves of the epidemic, as defined by their nadirs between national death rates—each approximately 3-4 months long, as shown in Figure 2 generated based on data from the COVID tracking project. As shown in Table 3, we will initiate surveys of Veterans who have survived their initial SARS-CoV-2 infection. The viral infection "index date" will be defined as date of each patient's first positive test. This will be a longitudinal survey such that once we start surveying a Veteran, that same Veteran will be surveyed in later waves as well—we will not "resample" between, for example, the 12- and 24-month surveys.

Comparators: To support causal inference, we will also sample Veterans without COVID who are matched to participants with COVID-19. In general, cases will be compared to comparators matched on risk of developing COVID infection during a given wave, incorporating geography at the VAMC and VISN level to take into account spatiotemporal heterogeneity and small area variations. There are certain nuanced issues around precise definitions of pseudo-index dates for comparators, and particularly avoiding immortal time bias, to which we will closely attend during implementation with the input of the Methods Core. In general, we will use coarsened exact matching or propensity scores to ensure balance on key measurable covariates, both of which our group has substantial experience with.

Table 3: Example of a Timeline of Cohorts for Survey Operations. Dates on the left indicate when the COVID-19 infection occurred. Dates on the top indicate when the survey would be done. Blocks of similar surveys are shaded. The numbers 12, 18, 24, etc. represent how many months after infection each survey is, to evaluate longitudinal changes over time.

			CORC	Calenda	r Time						year 2	->											year 3-	.>	
			2021				2022												2023						
COVID Infection Date			Septer	Octobe I	Vovem	Decem	Januar	Februa	March	April	May	June	July	Augus	Septe	Octob	Novem	Decem	Janua	Februa	March	April	May	June	July
2020	March	400 COVID	18	18					24	24					30	30					36	36			
"Vanguard"	April	200 Comparison		18	18					24	24					30	30					36	36		
	May	Each Surveyed 4x			18	18					24	24					30	30					36	36	
	June	Lacii Surveyeu 47	•			18	18					24	24	ı				30	30					36	36
	July																								
"Summer"	August																								
	September																								
	October																								
"Predictable"	November	400 COVID			12	12					18	18	}				24	24							
		200 Comparison				12	12					18	18	3				24	24						
2021	January	Each Surveyed 3x					12	12					18	18	3				24	24					
	February	Lacii Surveyed 3x						12	12					18	18					24	24				
	March	400 COVID							12	12					18	18					24	24			
"Early Vaccine Era"	April	200 Comparison								12	12					18	18					24	24		
	May										12	12	!				18	18					24	24	
	June	Each Surveyed 3x										12	12	2				18	18					24	24

Sample Size: We will enroll up to 3,000 Veterans over the course of the survey, interviewing them each 2-4 times. This sample size is driven by power calculations needed to examine key subgroups of interest, including looking for differences across waves of COVID-19, and in racial and gender minority groups of keen interest to the VA's mission. Taking this sample size into consideration, our selection of measures emphasized continuous or multivalued outcomes over binary outcomes to increase statistical power.

Survey operations: Our primary survey administration mode, as in past work, will be computer-assisted telephone administration by highly trained surveyors using highly validated instruments. When telephone administration is not feasible, we will offer REDCap-administered mail surveys.

We have used this approach—primarily phone-based administration of instruments by highly trained VA employees with substantial support, understanding of Veterans' issues, and of VA safety protocols—successfully in VA Ann Arbor studies including ResCU 1, ResCU 2 (IIR's 13-079 and 17-045, Protocols 1597244 and 1597246).

We will minimize total survey error by random sampling from a group of Veterans known from the VA's CDW to ensure very high recruitment and retention rates—our group routinely exceeds recruitment rates of 80% in studies of recently critically ill patients or Veterans, with whom we have conducted over 4,000 interviews, including among individuals with substantial disability and cognitive impairment.⁴⁶ These high recruitment, retention, and survey completion rates have been achieved through careful attention to detail, stable diverse staff (some of whom are Veterans) in whom we invest in ongoing training, and with whom we engage in constant refinement of methods. These methods (including survey practices, personnel training, and customized database organization built in VA REDCap and integrated into staff calendaring and email) have been codified as Standard Operating Procedures upon which we will build.

REDCap: VA REDCap (Research Electronic Data Capture) is a web-based application hosted and maintained by the VA Informatics and Computing Infrastructure (VINCI) and VA Information Resource Center (VIReC). It is housed on a VINCI server physically located at the VA Austin Information Technology Center (AITC) in Austin, Texas and is available only on the VA network. REDCap data collection and management projects rely on a thorough study-specific data dictionary defined in an iterative self-documenting process. This includes a study-specific user rights management system administered by the Project Owner or Principal Investigator. REDCap (www.project-redcap.org) was developed specifically around HIPAA-Security guidelines. REDCap has been disseminated for use locally at other institutions and currently supports 1,700+ academic/non-profit consortium partners on six continents and over 305,000 research end-users.

Survey Measures: Our survey measure selection is driven by our conceptual agenda, ease of use, comparability with key other studies on COVID-19 and other relevant populations, and a pragmatic respect for our respondents' time and therefore the need to balance multiple competing potential measures in a sufficiently short survey. As such, we favor general purpose, brief instruments, even as we recognize the imperfections of such instruments for some specialist needs.

These survey measures are nearly all highly standard measures that have been used thousands of times in Veterans and other populations to ensure that they can be asked and answered reliably and without undue respondent burden.

Other Issues:

Performance of individual survey items will be closely monitored over time. Items will be considered for replacement if found to have significant ceiling/floor effects, disproportionate respondent burden, or diminished scientific interest as knowledge of COVID-19 evolves. Yet it is also recognized that comparability within and between cohorts is a key scientific advantage, and so core items that function well will be preserved to the extent possible.

Linkage to Aim 1 data: The scale of surveys needed to be completed, the importance of avoiding systematic non-response error, and the continuing disruption of mail service mean that written informed consent and written HIPAA authorizations are not practical. Instead, verbal informed consent and permission to link patients' survey responses with their EHR for research purposes will be obtained and recorded, allowing for full integration of survey and EHR and other sources of data. Note that this also means that we will be able to use linkages to reduce respondent burden in reporting early healthcare use.

Data Dissemination Strategy: Every six-months, beginning six months after the first survey is collected, updated releases of all structured survey items and basic summary scores will be released via VINCI for all VA investigators with appropriate permissions—but specific HIPAA-protected identifiers will not be included. The research information sheet and recruitment letter include the VA's recommended explicit language about this and the option to opt out.

Analytic Methods: Descriptive: We will summarize each of the outcomes listed in Table 2 for the patient cohort at each 6-month after the index illness. Summary statistics (mean, median, mode, range; frequency; missing data) will be reported in tabular and graphical format. Survey weights will be incorporated throughout to allow generalizability of estimates to the source Veteran population receiving VA primary care.

Analytic Methods: Variation in Survey Outcomes: A similar approach as in Aim 1 will be used for defining variation in key survey-reported outcomes, albeit with greater constraints on the number of covariates that can be included due to the more limited size of the survey sample. Multi-level models will be estimated after controlling for patient-level factors such as age, race, and summary Elixhauser comorbidity score⁴⁸, and nested within hospitals. Longitudinal growth curve models within respondents over time will be used, as we have before, to examine evolution of outcomes over time.

In general, we expect quite little missing data due to our prior experience with very high item-level completion in administering these specific instruments to Veterans after hospitalization. However, should this be a concern, we will use case-wise deletion or multiple imputation, depending on the frequency of missingness.

Analytic Methods: Causal Effects of COVID on Clinical Outcomes: Our primary causal scientific question is: "What is the effect of a COVID-19 infection compared to not having gotten a COVID-19 infection at that time on patient-reported financial and mental health functioning?"

Patients who experienced (and survived) COVID-19 will be matched to a comparator patient cohort. Causal inference is strengthened by the following strategies: (a) matching patients with and without COVID-19 on key patient characteristics, and ensuring that both groups had equal ability to be selected into the study (e.g., due to survival), (b) administering surveys on the same timeframe between COVID-19 patients and comparators, relative to a selected index date/time zero, (c) collecting sufficient data on key covariates that are unmeasured in the EHR and guided by directed acyclic graphs (DAGs) and other causal graphs generated in collaboration with the CORC's Methods Core, (d) accounting for those covariates through inverse probability of treatment weights or similar approaches.

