5.7 Study Evaluations

For Aim 1, using national VA electronic health record data from VINCI-CDW, we will obtain the results of all nasopharyngeal or oropharyngeal swabs performed for SARS-CoV-2 PCR at the time of data abstraction and identify positive (detected) versus negative results.

Potential predictor variables will be extracted as of the time of testing for SARS-CoV-2 (for risk factors/prediction of hospitalization) and also as of the time of hospitalization (for risk factors/prediction of ICU admission, mechanical ventilation or death).

Using VINCI-CDW data, we will identify the following potential predictors/risk factors which are suspected to be associated with adverse outcomes in COVID-19:

Demographic factors: age, race, ethnicity, sex, socioeconomic status (including data from USVETS),

VA consolidated community care datasets (that track use of non-VA care paid for by the VA through the FEE basis file and the Patient Integrity Tool - PIT)

Case management/care coordination (VA Consult Toolbox)

Vital signs: temperature, blood pressure, heart rate and oxygen saturation, CAN score

Geographic factors: state, county, rural/urban, geocoded home address and associated ambient air pollution, distance to VA primary care and hospital

Comorbidities: diabetes, hypertension, COPD, asthma, history of solid organ transplantation, chronic kidney disease, cirrhosis, obesity (BMI), congestive heart failure, stroke, cardiovascular disease, HIV.

Severity of illness: Measured using variables used to calculate the VA case severity index.¹⁴

Co-infection with other viral or bacterial pathogens: influenza A or B, respiratory syncytial virus, bacterial co-infection.

Laboratory tests: CBC with differential, low lymphocyte count and high neutrophil to lymphocyte ratio (implicated in early studies as predictor), comprehensive metabolic panel [electrolytes and liver function tests], albumin (low albumin implicated as adverse predictor), brain natriuretic peptide,

PT/INR, CRP, pro-calcitonin, magnesium, troponin and IL-6 (if available, implicated as marker of cytokine storm).

Medications that may worsen outcomes: immunosuppressives, immunomodulators, corticosteroids, angiotensin converting enzyme inhibitors (ACE-I), angiotensin receptor blockers (ARB), non-steroidal anti-inflammatory drugs (NSAIDS) and thiazolidinediones which may increase the ability of the virus to enter the cells by increasing the expression of ACE2 receptors.

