Functional Status and Pain: development of frailty or functional impairment (e.g., injurious falls, wheelchair use), cognitive impairment (dementia, delirium, memory clinic visits, prescriptions for anticholinergic agents) and reduced independence (e.g., inpatient rehabilitation, skilled nursing facility care, skilled home care and home-based primary care referrals) or new diagnoses of headache, joint pain, fibromyalgia, and chronic fatigue, as well as increase in number of comorbidities.

Text Integration utilities (TIU) notes: to support more details qualitative and quantitative analysis of the electronic health record, we will search text and develop natural language processing (NLP) algorithms using the VISA search tool within VINCI to study the content of documentation in the VA-wide electronic health records of cohort members. This will allow us to provide a rich description of the content of notes and create variables not available in structured data sources including information documentation related to care processes and interactions with the health care system. In order to understand the clinical context of the content of TIU notes, we will need to have access to the specialty/discipline and clinical role of the authors of clinical notes. While we will present extracts from the electronic health record in presentations and manuscripts, the names (e.g., patients, family members, clinicians, medical centers) and dates that appear in TIU notes will be removed from any materials presented or published outside the study team so that individual quotations cannot be traced to patients, providers or other individuals. In some instances, we will indicate the season (spring, summer, winter and fall) of the year that particular quotations appeared in patients' electronic health records so that quotations can be situated in the context of the evolving pandemic but will not record actual dates.

Medicare, Medicaid and USRDS linked Medicare data

We will obtain Medicare, Medicaid and USRDS linked Medicare enrollment, claims and survey data for 2018 through the most current year available through VIReC for all Veterans included in our SARS-CoV-2 treatment and comparison groups.

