Statistical Analysis Plan

COVID-19 Observational Research Collaboratory
NCT05394025

Updated: June 25, 2025

Background

In a previous study, we found Veterans with a first case of COVID-19 (between 2020 and 2021) did not report more limitations in instrumental activities of daily living (IADL) at 18-months after infection relative to comparators who were contemporaneously uninfected.

Aim

In this updated longitudinal analysis, we examine whether self-reported counts of IADL changed between infected and uninfected comparators over 18 additional months of follow-up (36 months after infection).

Study Design

Prospective cohort study design with repeated surveys at 18-, 24-, 30-, and 36- months.

Population

The cohort was sampled from a parent cohort of Veterans, assembled by the COVID-19 Observational Research Collaboratory, with a first documented case of COVID-19 between March 2020 and April 2021 and uninfected matched comparators. Veterans were required to have been enrolled in VHA care, been assigned a VA primary care team, and had one or more VA primary care visits in the two years prior to cohort construction. COVID-19 infections were ascertained through the VA COVID-19 Shared Data Resource (CSDR) and Medicare claims data. Otherwise, eligible Veterans without evidence of a documented infection were considered as uninfected comparators. From this parent cohort, we conducted a stratified random sample of 100 Veterans who tested positive for COVID-19 in October, November, December, February, March, and April 2021. Sampling was further stratified by US Census region and hospitalization status. Of the 600 patients with COVID-19 a total of 235 (39.2%) Veterans consented and completed surveys; 244 uninfected matched comparators completed surveys.

Exposure

First documented COVID-19 infection (positive PCR test or clinical note) was the primary exposure of interest. Veterans without a documented history of COVID-19 infection were eligible comparators. Extensive matching, done monthly, was used to ensure comparability between groups.

Outcome

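### Aim 2 severity groups count only VA admissions, so patients admitted only to community hospitals fall in the lowest group; severity comparisons are exposed, the SAP's IADL model is not

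*Protocol*

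**What the plan says.** Protocol 5.1 (Aim 2, Cases) uses stratified random sampling so that "cases are equally divided based on maximal severity of their acute COVID course in VA". The groups are formed "based on patterns of health care utilization within the first 30 days after initial infection with SARS-CoV-2" and are "not hospitalized in VA; hospitalized in VA but not mechanically ventilated; mechanically ventilated". The first two labels are limited to VA; the third carries no such limit of its own, although the lead-in does. The protocol gives two reasons for the design. One is that "sampling weights assure that the aggregated population results are still representative of the study population as a whole". The other is "ensuring adequate representation to support comparisons across these subgroups of interest", so the groups serve analysis as well as sampling.

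The same section says that care at non-VA sites is poorly captured in the VA record and that Medicare and Medicaid claims arrive with delay. It also counts VA community-based and contracted care as part of the record, makes all Aim 1 data linkable to the survey, and expects linkage to spare respondents questions about early healthcare use. Protocol 5.7 lists "VA consolidated community care datasets (that track use of non-VA care paid for by the VA" and states "We will obtain Medicare, Medicaid and USRDS linked Medicare enrollment, claims and survey data for 2018 through the most current year available". No section says whether any of these sources feeds the severity groups.

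Protocol 5.1 identifies cases in the VA's own COVID-19 data. The SAP (Population) goes further: "COVID-19 infections were ascertained through the VA COVID-19 Shared Data Resource (CSDR) and Medicare claims data". It stratifies sampling by hospitalization status without saying whether that means VA or any hospital, and names no ventilation stratum. The SAP's model (Analysis) compares infected with uninfected Veterans over time, adjusted for age, sex and CAN score.

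**The concern.** A Veteran whose only admission was to a community hospital was hospitalized for COVID-19 but is grouped with those who were not. The VA-only flag is least reliable for cases known through Medicare, because their care was billed outside VA.

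The Protocol's Introduction raises two severity questions: whether people with few acute symptoms have long-term consequences, and whether consequences depend on initial severity. Protocol 5.1 also plans causal moderation analyses. If hospitalized Veterans have worse outcomes, hiding some of them in the lowest group makes that group look worse than it is and brings the groups closer together. Both questions are then answered less cleanly than the planned data would allow.

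**Working it through.** The documents give no misclassification rate, no hospitalization rate and no power figure for severity comparisons, so there is no stated figure to reproduce. What follows sizes the problem on assumptions.

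**Assumed inputs.** h = share of cases truly hospitalized within 30 days (10%, 15%, 25%). s = share of those admitted only outside VA (20%, 35%, 50%). Strictly, h should refer to survivors who respond. Excess among hospitalized cases = 1.5 IADL limitations, and none among those not hospitalized. VA and non-VA admissions are assumed to have equal outcomes, and the VA-hospitalized group is assumed to be correct.

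**Contamination of the lowest group.** c = sh / (1 − h + sh). Middle case: 0.35 × 0.15 / (0.85 + 0.0525) = 0.0525 / 0.9025 = 5.8%. The observed contrast is the true contrast × (1 − c), and the false effect in the lowest group is 1.5 × c.

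**Cost of pooling reclassified Veterans with the VA-hospitalized group.** The protocol divides cases equally across groups and weights back. Simplify to two groups of 100. The weight of a lowest-group Veteran relative to a VA-hospitalized one is r = (1 − h + sh) / (h(1 − s)), and m = 100c Veterans move. The Kish effective size of the pooled group is (100 + mr)² / (100 + mr²). Middle case: r = 0.9025 / 0.0975 = 9.26, m = 5.82, giving 153.8² / 598.4 = 39.6.

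| h | s | c | False effect (items) | r | Effective n if pooled (from 100) |
|---|---|---|---|---|---|
| 10% | 20% | 2.2% | 0.03 | 11.5 | 40 |
| 10% | 50% | 5.3% | 0.08 | 19.0 | 20 |
| 15% | 35% | 5.8% | 0.09 | 9.3 | 40 |
| 25% | 20% | 6.3% | 0.09 | 4.0 | 78 |
| 25% | 50% | 14.3% | 0.21 | 7.0 | 50 |

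**Which remedy is better?** Compare the root mean squared error of the contrast, with outcome SD assumed to be 2 or 3:

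- VA-only groups: √[(1.5c)² + SD²(1/100 + 1/100)]
- pooled: √[SD²(1/effective n + 1/(100 − m))]
- separate category: √[SD²(1/100 + 1/(100 − m))]

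In the middle case these are 0.296, 0.379 and 0.287 for SD 2, and 0.433, 0.568 and 0.431 for SD 3. Pooling is worse than leaving the groups alone in all nine combinations of h and s, though only just at h = 25%, s = 50%, SD 2 (0.356 against 0.355). The separate category removes the bias and leaves the lowest group with 100 − m = 86 to 98 Veterans.

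**Wider inputs.** With h = 10% to 40% and 10% to 70% of admissions outside VA, c runs from 1.1% to 31.8%. A comparison with 80% power at c = 0 (two-sided alpha 0.05, assumed) falls to 76% at c = 5%, 71% at c = 10% and 48% at c = 31.8%.

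**The case against.** The strongest reply is that the VA-only rule is written for sampling, where delayed claims justify it, and that no section fixes a VA-only variable for analysis. The label is accurate as worded. VA-paid community care and claims are planned and linkable, so analysts may well use them. This stands in part: the sampling stratum is defensible. But the same sentence gives subgroup comparison as a purpose, and the only definition of those subgroups is the VA-only one. Late claims do not explain leaving them out when the analysis is run.

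A reader might infer that community admissions are analysed as mild COVID and that the study's main result is biased. The documents do not support this. No group is called mild. The SAP contains no severity term, subgroup or hospitalization contrast. Misplaced stratum membership does not by itself bias weighted overall estimates, because design weights follow the strata as sampled. Nor does any section show the VA-only groups being applied to Medicare-identified cases: those cases appear only in the SAP, whose hospitalization status may or may not be VA-only.

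Two further points stand. Severity is not among the examples of key subgroups in the protocol's sample-size paragraph, which names epidemic waves and racial and gender minorities. The 1.5-item excess has no support in the documents: the SAP's Background reports no more IADL limitations at 18 months among infected Veterans overall.

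**Conclusion.** The concern holds within limits. The protocol states a VA-only rule for groups it means to compare, although it plans data that could find many of the missing admissions; community ventilation and the SAP's hospitalization status are undefined. Severity-subgroup and moderation analyses are exposed, most plausibly to an overstated effect in the lowest group and a contrast reduced by about 2% to 14% (5.8% at the middle values).

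That range rests wholly on assumed h and s, on equal outcomes for VA and non-VA admissions, and on a correct VA-hospitalized group. The item-scale figures also need the assumed 1.5-item excess. The size in this study cannot be determined from the documents. The infected-versus-uninfected IADL result is untouched. This is a minor, inexpensive improvement.

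**What to change.** - State in the protocol and SAP which sources define hospitalization status, and how ventilation in a community hospital is classed.
- For every severity-subgroup or severity-adjusted analysis, identify 30-day hospitalization and ventilation from VA, VA-paid community care, Medicare and Medicaid records together.
- Take Veterans with a non-VA admission out of the lowest group, report them as a separate category, and give the number reclassified. That count also measures the problem.
- Keep the VA-only strata for computing sampling weights.
- Pool the separate category with the VA-hospitalized group only as a sensitivity analysis, with the effective sample size shown.

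The cost is some wording, a modest linkage task on data already planned, and a slightly smaller lowest group. The separate category will probably be too small for firm conclusions of its own. Admissions that reach none of these payers will still be missed, so some misclassification will remain and will depend on insurance coverage.
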